4.2.2.2 Supportive secondary endpoints

Supportive secondary efficacy endpoints:

- Responder after 26 weeks (Yes/No) for:
 - $HbA_{1c} < 7.0\% *$

 Protocol
 Date:
 20 November 2015
 Novo Nordisk

 Trial ID: NN9068-4229
 Version:
 2.0

 UTN: U1111-1168-9343
 Status:
 Final

Page:

19 of 107

 \circ HbA_{1c} < 7.0% without weight gain

- o HbA_{1c} < 7.0% without treatment-emergent severe or BG confirmed symptomatic hypoglycaemic episodes during the last 12 weeks of treatment
- \circ HbA_{1c} < 7.0% without treatment-emergent severe or BG confirmed symptomatic hypoglycaemic episodes during the last 12 weeks of treatment and without weight gain
- \circ HbA_{1c} \leq 6.5%

EudraCT No.: 2015-001596-48

- o HbA_{1c} \leq 6.5% without weight gain
- O HbA_{1c} \leq 6.5% without treatment-emergent severe or BG confirmed symptomatic hypoglycaemic episodes during the last 12 weeks of treatment
- \circ HbA_{1c} \leq 6.5% without treatment-emergent severe or BG confirmed symptomatic hypoglycaemic episodes during the last 12 weeks of treatment and without weight gain
- Change from baseline after 26 weeks in:
 - Waist circumference
 - Fasting plasma glucose (FPG)*
- Fasting lipid profile
 - Cholesterol
 - o Low-density lipoprotein cholesterol (LDL cholesterol)
 - High-density lipoprotein cholesterol (HDL cholesterol)
 - o Very-low-density lipoprotein cholesterol (VLDL cholesterol)
 - o Triglycerides
 - o Free fatty acids
- Self-measured plasma glucose (SMPG) 9-point profile
 - o 9-point profile
 - Mean of the 9-point profile
 - Prandial plasma glucose increments (from before meal to 90 min after breakfast, lunch and dinner). The mean increment over all meals will be derived as the mean of all available meal increments
- Vital signs
 - Systolic and diastolic blood pressure

Supportive secondary safety endpoints:

- Number of treatment-emergent adverse events during 26 weeks*
- Number of treatment-emergent nocturnal severe or BG confirmed symptomatic hypoglycaemic episodes during 26 weeks
- Number of treatment-emergent hypoglycaemic episodes according to ADA definition during 26 weeks
- Change from baseline in clinical evaluation after 26 weeks:
 - o Electrocardiogram (ECG)

- Eye examination
- o Physical examination
- o Pulse rate
- Change from baseline in laboratory assessments after 26 weeks:
 - o Biochemistry
 - o Haematology
 - o Calcitonin
 - Urine albumin/creatinine ratio

Supportive secondary health economics endpoints:

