- In the fourth step, for each of the 1000 copies of the dataset, missing HbA_{1c} values at the second planned HbA_{1c} measurement visit after randomisation (V14) are imputed in the same way as in the previous step, now based on an ANOVA model with pre-trial OAD and region as factors, and the HbA_{1c} values at baseline and at previous planned HbA_{1c} measurement visits as covariates, fitted to the control group (IGlar) and subjects with retrieved (V32A) data in the investigational group (IDegLira)
- This fourth step is then repeated sequentially over visits where HbA_{1c} measurement is planned, adding one visit in each step until the last planned visit (V32)
- In the sixth step a penalty equal to the non-inferiority margin 0.3% is added to the EOT HbA_{1c} value for any prematurely discontinued subject in the investigational group (IDegLira), irrespective of the EOT value being retrieved (V32A) data or an imputed value from the sequential imputation steps (step 3 to 5)

• In the seventh step, for each of the 1000 complete data sets, the change from baseline to the EOT visit (V32) is analysed using an ANOVA model with treatment, pre-trial OAD and region as factors and baseline HbA_{1c} value as a covariate

• In the eighth step, the estimates and standard errors for the 1000 data sets are pooled to one estimate and associated standard error using Rubin's rule³⁷. From these pooled estimates the confidence interval for the treatment difference and the associated *p*-value are calculated

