Responder for HbA_{1c} without treatment-emergent severe or BG confirmed symptomatic hypoglycaemic episodes and weight gain after 26 weeks will be defined as

- HbA_{1c} < 7.0%without treatment-emergent severe or BG confirmed symptomatic during the last 12 weeks of treatment, and change in body weight from baseline \leq 0 kg
- HbA $_{1c} \le 6.5\%$ without treatment-emergent severe or BG confirmed symptomatic during the last 12 weeks of treatment, and change in body weight from baseline ≤ 0 kg

Theses endpoints will be analysed as the composite HbA_{1c} and weight responder endpoints, where subjects with less than 12 weeks of treatment conservatively will be set to being non-responder.

Waist circumference change from baseline after 26 weeks

Change from baseline in waist circumference will be analysed by multiple imputation J2R.

Fasting plasma glucose change from baseline after 26 weeks

Change from baseline in FPG will be analysed by multiple imputation J2R.

CONFIDENTIAL

Date: Version: Status: Page:

20 November 2015 | Novo Nordisk 2.0 Final 82 of 107

Fasting lipid profile after 26 weeks

Cholesterol, LDL cholesterol, HDL cholesterol, VLDL cholesterol, triglycerides and free fatty acids will be analysed separately by multiple imputation J2R. In these statistical analyses, the endpoint will be log-transformed and so will the corresponding baseline covariate.

Self-measured plasma glucose (SMPG) 9-point profile change from baseline after 26 weeks

The following six endpoints from the 9-point SMPG profile will be defined:

- 9-point profile (individual SMPG values). [One endpoint]
- Mean of the 9-point profile, defined as the area under the profile (calculated using the trapezoidal method) divided by the measurement time. [One endpoint]
- Prandial plasma glucose increments (from before meal to 90 min after meal for breakfast, lunch and dinner). The mean increment over all meals will be derived as the mean of all available meal increments. [Four endpoints]

A linear mixed effect model will be fitted to the 9-point SMPG profile data. The model will include treatment, pre-trial OAD, time (within 9-point profile), the interaction between treatment and time, the interaction between pre-trial OAD and time as fixed factors, and subject as random effect. From the model mean profile by treatment and relevant treatment differences will be estimated and explored.

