Change from baseline in mean of the 9-point profile and prandial increment endpoints will be analysed separately by multiple imputation J2R.

Blood pressure (systolic and diastolic) change from baseline after 26 weeks

Change from baseline in systolic and diastolic blood pressure will be analysed separately by multiple imputation J2R.

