2.24 Section 17.4.2.1 Efficacy endpoints

For each of the multiple copies (1000) of the full dataset of the primary analysis of the primary estimand (unconditional multiple imputation J2R with retrieved data, NI penalty section 2.19) the responder endpoints are derived without using the non-inferiority penalty (step 6) and analysed with the standard logistic regression model. Estimates are pooled using Rubin's rule³/.

Waist circumference change from baseline after 26 weeks

Change from baseline in waist circumference will be analysed by unconditional multiple imputation J2R.

Fasting plasma glucose change from baseline after 26 weeks

Change from baseline in FPG will be analysed by *unconditional* multiple imputation J2R.

Fasting lipid profile after 26 weeks

Cholesterol, LDL cholesterol, HDL cholesterol, VLDL cholesterol, triglycerides and free fatty acids will be analysed separately by *unconditional* multiple imputation—J2R. In these statistical analyses, the endpoint will be log-transformed and so will the corresponding baseline covariate.

Self-measured plasma glucose (SMPG) 9-point profile change from baseline after 26 weeks

A linear mixed effect model will be fitted to the 9-point SMPG profile data. The model will include treatment, pre-trial OAD, time (within 9-point profile), the interaction between treatment and time, the interaction between pre-trial OAD and time as fixed factors, and subject as random effect, where measurements within subjects will be assumed correlated as specified by a compound symmetric covariance matrix. From the model mean profile by treatment and relevant treatment differences will be estimated and explored.

Change from baseline in mean of the 9-point profile and prandial increment endpoints will be analysed separately by *unconditional* multiple imputation-J2R.

Blood pressure (systolic and diastolic) change from baseline after 26 weeks

Change from baseline in systolic and diastolic blood pressure will be analysed separately by unconditional multiple imputation J2R.

Protocol Amendment 2 Trial ID: NN9068-4229 UTN:U1111-1168-9343

EudraCT No.: 2015-001596-48

CONFIDENTIAL

Date: Version: Status: Page:

28 November 2016 | Novo Nordisk Final 18 of 19

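### The mixed model for the individual 9-point SMPG values omits baseline SMPG, although a baseline profile is collected

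*Protocol*

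**What the plan says.** Section 17.4.2.1 defines six endpoints from the SMPG profile. The first is "9-point profile (individual SMPG values). [One endpoint". It gets its own linear mixed model: "The model will include treatment, pre-trial OAD, time (within 9-point profile), the interaction between treatment and time", then pre-trial OAD by time, with subject as random effect. The stated output is: "From the model mean profile by treatment and relevant treatment differences will be estimated and explored". Amendment 2, section 2.24, reopens this sentence and adds only "where measurements within subjects will be assumed correlated as specified by a compound symmetric covariance matrix".

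The other five SMPG endpoints are handled differently: "Change from baseline in mean of the 9-point profile and prandial increment endpoints will be analysed separately by multiple imputation". That method is modelled on section 17.3.1, whose final step is an "ANOVA model with treatment, pre-trial OAD and region as factors and baseline HbA_{1c} value as a covariate".

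The group heading in section 17.4.2.1 reads "Self-measured plasma glucose (SMPG) 9-point profile change from baseline after 26 weeks". The endpoint list in section 4.2.2.2 has only "Self-measured plasma glucose (SMPG) 9-point profile" and names the individual profile without the word change.

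Sections 8.1 (Diaries) and 8.4.4 require a 9-point profile within the week before V2, V18 and V32, so a pre-randomisation profile exists.

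**The concern.** The term list is explicit and was revisited in an amendment, so the protocol itself fixes the model. Baseline cannot enter by another route. The only time factor is position within the profile, there is no visit term, and section 17 limits statistical analysis to endpoints after 26 weeks. The baseline profile is therefore neither a covariate nor part of the response vector.

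This departs from the protocol's own practice without a stated reason. Insulin dose, which has no baseline of its own, is given baseline HbA1c instead (section 17.4.1.1). The treatment differences at single time points would be unadjusted, while the profile mean and meal increments derived from the same measurements would be baseline-adjusted.

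What is at stake is the width of the confidence intervals at each time point. There is no question of bias or of type I error.

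**Working it through.** **Baseline covariate in the other continuous models**

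- HbA1c: stated (17.3.1, final ANOVA; 17.3.2, standard MMRM).
- Lipids: stated, log-transformed (17.4.2.1).
- Body weight: by substitution in the HbA1c model (17.4.1.1).
- Waist, FPG, profile mean, meal increments, blood pressure, pulse, PRO scores: by reference to the multiple imputation model (17.4.2.1, 17.4.2.2, 17.5).
- Insulin dose: baseline HbA1c as substitute (17.4.1.1).
- Individual 9-point SMPG values: none.

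**Cost in precision.** The plan gives no figure to reproduce. Inputs:

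- n = 354/2 = 177 per arm, from the expected completers in section 6.1.
- SD = 1 at each time point, so results are in SD units.
- r, the correlation of baseline and week-26 values at the same time point, is not in the documents. The assumed range is 0.1 to 0.5. Low values are included because both arms are titrated to the same pre-breakfast target (section 5.3).

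*Week-26 value as response.* Without baseline, SE = sqrt(2/177) = 0.1063 and the 95% half-width is 1.96 × 0.1063 = 0.208. With baseline at the same time point the variance is multiplied by 1 − r², so the SE cut is 1 − sqrt(1 − r²).

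*Change as response, equal SDs at both visits.* The unadjusted variance is proportional to 2(1 − r). The adjusted variance is again proportional to 1 − r². The ratio is (1 + r)/2, so the SE cut is 1 − sqrt((1 + r)/2).

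| r | SE cut, value | Half-width after, value | SE cut, change |
|---|---|---|---|
| 0.1 | 0.5% | 0.207 | 25.8% |
| 0.2 | 2.0% | 0.204 | 22.5% |
| 0.3 | 4.6% | 0.199 | 19.4% |
| 0.4 | 8.3% | 0.191 | 16.3% |
| 0.5 | 13.4% | 0.180 | 13.4% |

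**Simulation of the nine-point model.** Settings: 1000 trials per r, week-26 value as response, compound symmetric covariance, within-visit correlation 0.5 (assumed), terms for time, treatment by time and baseline by time; pre-trial OAD left out.

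- (a) Baseline correlates r with its own time point and 0.5r with the others: empirical SE cut 0.4 / 1.6 / 5.4 / 9.0 / 14.6% for r = 0.1 to 0.5; model-based cut 0.5 / 2.0 / 4.7 / 8.3 / 13.4%. This agrees with the formula.
- (b) Every baseline point correlates r with every week-26 point: empirical cut 0.2 / 0.6 / 1.5 / 3.2 / 6.0%.

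In case (b) the baseline profile mean would be the stronger covariate. Its variance is (1 + 8 × 0.5)/9 = 0.556, so R² = r²/0.556. At r = 0.5, R² = 0.45 and the SE cut is 1 − sqrt(0.55) = 25.8%.

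Refitting with change as response and baseline by time in the model gave the same treatment differences to within 1e-14.

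**The case against.** The strongest reply is that nothing here is invalid. The model gives unbiased estimates and correct intervals. Its declared purpose is to estimate and explore. The endpoint is outside the hierarchy in section 17.4.1 and is not one of the key endpoints marked for disclosure. The profile mean and increments already give a baseline-adjusted comparison of the same data. All of that stands, and it is why the point is minor.

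It is also true that r is unknown, that at low r the gain on the week-26 value is negligible, and that for several endpoints the baseline covariate is read across from the HbA1c model and not written out. That reading is nonetheless the natural one.

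A further objection is that the size depends on which response and which form of covariate are chosen. This is correct: about 13% is the upper end only for the week-26 value, the same-time-point covariate and r up to 0.5. The alternatives in the working (change as response, or the baseline profile mean in case (b)) give larger gains, up to about 26%, so the dependence does not weaken the case for adjusting.

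Finally, the covariate brings nine slopes and a need to handle missing baseline profiles. That cost is real but small.

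**Conclusion.** The concern holds as a low-priority improvement. The protocol fixes a model that leaves out a baseline measurement the trial collects, and this is the only modelled continuous endpoint so treated. The consequence is precision alone.

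The likeliest reading of the response is the week-26 value, since the endpoint is defined as individual values and the output is a mean profile. On that reading the same-time-point covariate would reduce the SE by somewhere between a negligible amount and about 13%, for r between 0.1 and 0.5 and 177 subjects per arm. If change is meant, the unadjusted model loses more: 13% to 26% over the same range. Primary and confirmatory conclusions are unaffected.

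The model also omits region, which the other models include. That is minor, since section 11 states that randomisation is not stratified.

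**What to change.** In section 17.4.2.1, add the baseline SMPG value at the same time point and its interaction with time as fixed effects, and add region for consistency with the other models.

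Name the response so that the group heading and the endpoint definition agree. With baseline by time in the model, value and change give the same treatment differences, so the choice is one of presentation. Naming the week-26 value matches the endpoint definition.

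Before database lock, specify an arm-blind rule for a missing baseline profile, for example imputing the covariate by its mean over both arms at that time point. The screening fallback in section 17 cannot serve, because no 9-point profile is taken at screening.

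The cost is a few words in one supportive model and this one rule. No new data are needed, and the primary and confirmatory analyses do not change.

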17.4.2.2 Safety endpoints

Adverse events during 26 weeks

AEs will be coded using the most recent version of the Medical Dictionary for Regulatory Activities.

A treatment-emergent AE (TEAE) is defined as an event that has onset date on or after the first day of exposure to randomised treatment and no later than 7 days after the last day of randomised treatment. If the event has onset date before the first day of exposure on randomised treatment and increases in severity during the treatment period and until 7 days after the last drug date, then this event should also be considered as a TEAE. Major adverse cardiovascular events (MACEs) are considered treatment-emergent until 30 calendar days after the last day of randomised treatment.

TEAEs are summarised descriptively, whereas non-TEAEs are presented in listings. TEAE data will be displayed in terms of the number of subjects with at least one event (N), the percentage of subjects with at least one event (%), the number of events (E) and the event rate per 100 years of exposure (R).

Summaries of TEAEs and of serious TEAEs will be presented as an overview including all AEs, serious AEs, number of deaths, AEs by severity, AEs by relation to treatment and AEs of special interest including AEs leading to treatment discontinuation or withdrawal.

Furthermore summary tables based on system organ class and preferred terms are made for:

- All TEAEs
- Serious TEAEs
- TEAEs possibly or probably related to trial product
- Severe, moderate and mild TEAEs
- TEAEs reported by safety areas of interest
- TEAEs with preferred term that are experienced by at least 5% (1%) of the subjects in any treatment arm or by at least 5% (1%) of all subjects

A listing for non-TEAEs with onset date before the first day of exposure to randomised treatment will be presented. A listing will also be presented for non-TEAEs collected after the treatment-emergent period according to the definition of TEAE.

Additional summaries will be displayed for MACEs collected between the end of treatment (V32) and the last follow-up visit (V32A) for subjects who discontinue trial product prematurely.

Hypoglycaemic episodes during 26 weeks

For the definition and classification of hypoglycaemic episodes refer to section 17.4.2.3.

Data on treatment-emergent hypoglycaemic episodes are presented in terms of the number of subjects with at least one event (N), the percentage of subjects with at least one event (%), the number of events (E) and the event rate per 100 years of exposure (R).

Separate summaries are made by severity considering severe or BG confirmed symptomatic hypoglycaemic episodes, severe or BG confirmed hypoglycaemic episodes, and the ADA (American Diabetes Association) classification of hypoglycaemia. The summaries are made for all and nocturnal (between 00:01 and 05.59 both inclusive) episodes respectively.

Number of nocturnal treatment-emergent severe or BG confirmed symptomatic hypoglycaemic episodes during 26 weeks will be analysed using the same J2R multiple imputation model as used for the treatment-emergent severe or BG confirmed symptomatic hypoglycaemic episodes.

| Protocol | Date: 20 November 2015 | Novo Nordisk | Version: 2.0 | Status: Final |

Page:

84 of 107

Clinical evaluation (ECG, eye examination and physical examination) change from baseline after 26 weeks

Eye examination (fundoscopy/fundusphotography) and 12-lead ECG findings will be summarised descriptively, including:

Summaries for each visit

EudraCT No.: 2015-001596-48

• Shift tables from baseline to after 26 weeks

Pulse rate change from baseline after 26 weeks

Change from baseline in pulse rate will be analysed by multiple imputation J2R.

Laboratory assessments (Biochemistry, Haematology, Calcitonin and urine analysis)

All laboratory parameters will be summarised descriptively including

- Summaries by visit
- Shift tables from baseline to after 26 weeks
- Proportion of subjects with measurements outside reference range by treatment and week
- Box plots by time since randomisation
- Listings of individual values outside reference ranges (abnormal values)

For lipase and amylase the following rule applies in the evaluation of the result:

• If the amylase or lipase baseline (at screening) value is > 3×upper normal range (UNR) the information will be regarded as medical history for that subject

17.4.2.3 Classification of hypoglycaemia

Treatment-emergent: hypoglycaemic episodes will be defined as treatment-emergent if the onset of the episode occurs on or after the first day of trial product administration, and no later than 7 calendar days after the last day on trial product.

Nocturnal hypoglycaemic episodes: are episodes occurring between 00:01 and 05.59 both inclusive.

Hypoglycaemic episodes are classified according to the Novo Nordisk classification of hypoglycaemia (see Figure 17–1) and the ADA classification of hypoglycaemia (see Figure 17–2).

[figure not shown]
Novo Nordisk classification of hypoglycaemia

In normal physiology, symptoms of hypoglycaemia occur below a plasma glucose level of 3.1 mmol/L $(56 \text{ mg/dL})^{39}$. Therefore, Novo Nordisk has included hypoglycaemia with plasma glucose levels below this cut-off point in the definition of BG confirmed hypoglycaemia.

Protocol	CONFIDENTIAL	Date:	20 November 2015	Novo Nordisk
Trial ID: NN9068-4229		Version:	2.0	
UTN: U1111-1168-9343		Status:	Final	
EudraCT No.: 2015-001596-48		Page:	85 of 107	

Novo Nordisk uses the following classification (see Figure 17–1) in addition to the ADA classification:

- Severe hypoglycaemia according to the ADA classification
- Symptomatic BG confirmed hypoglycaemia: An episode that is BG confirmed by plasma glucose value <3.1 mmol/L (56 mg/dL) with symptoms consistent with hypoglycaemia
- Severe or BG confirmed symptomatic hypoglycaemia: An episode that is severe according to the ADA classification²⁴ or BG confirmed by a plasma glucose value <3.1 mmol/L (56 mg/dL) with symptoms consistent with hypoglycaemia

Note: Glucose measurements are performed with capillary blood calibrated to plasma equivalent glucose values

Figure 17–1 Novo Nordisk classification of hypoglycaemia

[figure not shown]
20 November 2015 Novo Nordisk Protocol Date: Trial ID: NN9068-4229 Version: 2.0 CONFIDENTIAL UTN: U1111-1168-9343 Final Status: 86 of 107

Page:

ADA classification $\frac{24}{2}$ of hypoglycaemia

EudraCT No.: 2015-001596-48

- Severe hypoglycaemia: An episode requiring assistance of another person to actively administer carbohydrate, glucagon, or take other corrective actions. Plasma glucose concentrations may not be available during an event, but neurological recovery following the return of plasma glucose to normal is considered sufficient evidence that the event was induced by a low plasma glucose concentration
- Asymptomatic hypoglycaemia: An episode not accompanied by typical symptoms of hypoglycaemia, but with a measured plasma glucose concentration ≤ 3.9 mmol/L (70 mg/dL)
- Documented symptomatic hypoglycaemia: An episode during which typical symptoms of hypoglycaemia are accompanied by a measured plasma glucose concentration ≤ 3.9 mmol/L (70 mg/dL)
- Pseudo-hypoglycaemia: An episode during which the person with diabetes reports any of the typical symptoms of hypoglycaemia with a measured plasma glucose concentration > 3.9 mmol/L (70 mg/dL) but approaching that level
- Probable symptomatic hypoglycaemia: An episode during which symptoms of hypoglycaemia are not accompanied by a plasma glucose determination but that was presumably caused by a plasma glucose concentration < 3.9 mmol/L (70 mg/dL)

Note: Glucose measurements are performed with capillary blood calibrated to plasma equivalent glucose values

Figure 17–2 ADA classification of hypoglycaemia

Protocol
Trial ID: NN9068-4229
Version:
20 November 2015 | Novo Nordisk
Version:
2.0

